Quantitative Data Analysis Plan In testing the efficacy the HoMBRES de Familia intervention, we will utilize a 2-arm RCT employing intent-to-treat analysis using the initial group assignment, without considering the number of sessions that participants attend. We will run descriptive analyses at baseline for sociodemographic variables including age, country of birth, education, income, and marital status, and assess the differences between intervention group and control group at baseline using t-test for continuous variables and Chi-square test for categorical variables. We will test the efficacy of the intervention on individual outcomes (substance use, family violence, HIV) to examine how each component of the SAVA syndemic was independently impacted. We will use linear mixed model for continuous outcomes and generalized linear mixed model for categorical outcomes at follow-up, while adjusting for baseline measures, sociodemographics, and potential cluster effect among groups in intervention group and father-son dyads.

Page 12 of 23 Revised: March 23, 2020

IRB Study Number: Version HoMBRES de Familia (HoMBRES) #1

13) Provisions to Monitor the Data to Ensure the Safety of Subjects*

All aspects of the Research Project implementation will be governed by Research Project Lead ([name]) with assistance of Project Co-Lead ([name]) or Project Coordinator ([name]) under the monitoring of the Protocol PI ([name], formerly known as [name]). Data quality assurance procedures will be done by a trained staff member. Researchers will monitor and follow-up and report as required suicidality ideation and child as well as elderly abuse. The study will be monitored by the CLaRO Study Monitoring Unit which is based at the UM School of Nursing and Health Studies. The Study Monitoring Unit will (1) verify compliance with regulatory requirements, (2) ensure that the Project Leads and staff (including those at community agencies) are fully informed of regulatory requirements and properly trained to perform the duties assigned, and (3) monitor procedures to prevent errors and minimize protocol deviations that can negatively affect quality of the data collected and compromise human subjects' protection. The project will have a quality assurance (QA) review: prior to initiation, upon conducting baseline procedures with the first wave of study participants; and bi-annually for interim reviews.

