Project Lead or CO- Project Lead are responsible for conducting further evaluations and completion of the AE log.

In addition to the SAE's listed above, SAEs will include all issues that involve imminent danger to self or other. In cases of current suicidal, homicidal, and abusive behaviors, participants in both conditions will be immediately referred to the Open-Door clinic or to the local emergency room in order to ensure that appropriate crisis intervention services are provided. The reporting procedures for SAEs experienced by any participant in the study will be in accordance with the UM IRB reporting policy. When an SAE occurs, the Project Lead and the PI must be notified when possible within 2 hours of identification. The PI, in consultation with the Project Lead will be responsible for assessing relatedness to the intervention and forwarding the report to the UM IRB and NIH as required.

Safety will be assessed using two principal Safety Assessment Strategies: (1) incident and adverse event monitoring through a passive system, which will entail reporting using a form that details the various reportable event categories, and an (2) active system, whereby [name] will, on a weekly basis, determine if any reportable events occurred. The events reportable through the active and passive adverse event monitoring system include: (a) unauthorized disclosures or breaches of confidentiality; (b) threats or acts of violence or self-harm; (c) acts of negligence and violence against a minor or an elderly person. Interviews with participants will ensure the report of suicidal ideation, family violence, or other sentinel events.

14) Withdrawal of Subjects*

Subjects may choose to withdraw from the study at any time. We will discontinue data collection on the withdrawn subject and will use the partial data collected with participant's permission. Participants will be told that their participation in the study may be stopped at any time by the investigator without their permission. Subjects will be withdrawn by the PI (in consultation with the Project Lead) if their safety is endangered by attending the intervention groups. Reasons for withdrawal may be if the participant appears to be extremely distraught by the discussion in the group sessions or if the participant threatens to harm himself or others.

15) Risks to Subjects*

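### Section 14 does not separate stopping sessions from leaving the study, so a father removed by the PI may lose his only follow-up outcome: a small bias risk of uncertain direction, cheap to close

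*Combined protocol and SAP*

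**What the plan says.** Section 14 (Withdrawal of Subjects) opens with the participant's right to leave the study. It then says "We will discontinue data collection on the withdrawn subject" and that the team "will use the partial data collected with participant's permission". Next, participants are to be told that "their participation in the study may be stopped at any time by the investigator without their permission". After that comes removal for safety: "Subjects will be withdrawn by the PI (in consultation with the Project Lead) if their safety is endangered by attending the intervention groups". The reasons offered are that the participant is "extremely distraught by the discussion in the group sessions or if the participant threatens to harm himself or others". No separate data rule is given for a father removed in this way.

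Section 12 (Quantitative Data Analysis Plan) describes a two-arm trial "employing intent-to-treat analysis using the initial group assignment, without considering the number of sessions that participants attend". The models are a linear mixed model for continuous outcomes and a "generalized linear mixed model for categorical outcomes at follow-up", adjusted for baseline, sociodemographics and clustering.

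Section 10 plans outcome assessments at baseline and 6 months only. The telephone contact at 2-3 months asks a few open questions and does not measure the outcomes. Control sessions leave out SAVA topics. Section 13 adds that, in cases of suicidal, homicidal or abusive behaviour, "participants in both conditions will be immediately referred to the Open-Door clinic" or to the local emergency room.

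**The concern.** Intent-to-treat needs outcomes from everyone randomised, whether or not they finish the sessions. Section 12 secures half of this: it disregards attendance. It does not say what happens to a father who has no outcome. Because the models use the outcome at follow-up, a father without a 6-month value adds nothing to the comparison on that outcome.

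If removal by the PI ends data collection, the outcomes lost are not a random subset. One reason for removal is distress at the session content, and only the HoMBRES sessions cover SAVA topics, so that reason could arise more often in that arm. The other is a threat of harm, which plausibly relates to family violence, one of the outcomes under test. Unequal removal of fathers whose outcomes differ would bias the comparison by assigned arm. An outcome that was never collected cannot be recovered at analysis.

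**Working it through.** **Reading the text.** Three features favour the wide reading, in which the data stop covers fathers removed by the PI. The same verb is used for both routes. The investigator is said to stop participation in the study, not merely in the sessions. No other data rule is given. Two features favour the narrow reading: the data-stop sentence directly follows voluntary withdrawal, and it ends with the participant's permission. Section 12 does not settle the matter, because it addresses sessions missed, not outcomes missed.

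**Inputs.** The documents give 160 dyads (Section 6). They give no allocation ratio, SD, removal rate or power calculation in the sections available, so there is no plan figure to reproduce. Assumed: 1:1 allocation (80 fathers per arm), no true effect, one continuous outcome in SD units, two-sided 5% test, clustering ignored, and no 6-month value for removed fathers. Removed fathers are on average d SD worse than the arm average, with d = 0.5, 1.0 or 1.5.

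**Formulas.** With kH removed from HoMBRES and kC from control:

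- bias = kH·d/(80 − kH) − kC·d/(80 − kC)
- SE = √[1/(80 − kH) + 1/(80 − kC)]
- type I error = Φ(−1.96 + bias/SE) + Φ(−1.96 − bias/SE)

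Example, 8 v 0 with d = 1: bias = 8/72 = 0.111; SE = √(1/72 + 1/80) = 0.162; ratio 0.684; type I error 10.5%.

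| Removed (HoMBRES v control) | Bias at d = 1 (SD) | SE | Type I error at d = 0.5 / 1.0 / 1.5 |
|---|---|---|---|
| 1 v 0 | 0.013 | 0.159 | 5.0 / 5.1 / 5.2% |
| 2 v 0 | 0.026 | 0.159 | 5.1 / 5.3 / 5.7% |
| 4 v 2 | 0.027 | 0.161 | 5.1 / 5.3 / 5.7% |
| 4 v 0 | 0.053 | 0.160 | 5.3 / 6.2 / 7.8% |
| 8 v 2 | 0.085 | 0.163 | 5.8 / 8.2 / 12.3% |
| 8 v 0 | 0.111 | 0.162 | 6.4 / 10.5 / 17.7% |
| 8 v 8 | 0 | 0.167 | 5.0 / 5.0 / 5.0% |

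**Direction.** If removed fathers are worse, losing them flatters HoMBRES. If they do better, for instance after referral, the sign reverses: 8 v 0 with d = −0.5 gives a bias of −0.056 SD and type I error of 6.4%.

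**Definition of the gap.** If D is measured against retained fathers instead of the arm average, the 8 v 0 bias at 1 SD is 0.10 × 1 = 0.10 SD, and type I error is 9.4%.

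**Baseline adjustment.** In simulation (40,000 trials per setting, removal more likely with a worse outcome, removed fathers 1.00-1.12 SD worse, baseline correlation 0.5), adjustment lowers type I error for 8 v 0 from 11.2% to 9.5% and for 8 v 2 from 8.9% to 7.8%. For 2 v 0 the adjusted figure is 5.3%. At correlation 0.7, 8 v 0 gives 8.3%. This gain depends on baseline explaining part of the gap. If a full 1 SD remained after adjustment, the smaller residual SD would work the other way: 0.10/0.141 = 0.71 SE (11.0%) at correlation 0.5, and 0.10/0.116 = 0.86 SE (13.9%) at 0.7.

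**The case against.** The best defence is that the narrow reading is reasonable and the issue may never arise in numbers. The data-stop sentence belongs grammatically to voluntary withdrawal, and nothing states outright that a father removed by the PI is not followed. Section 15 expects minimal risk and has participants told to speak in the third person. Sections 10 and 21 move delivery to video links, which leaves less room for distress in group discussion, although Section 8 still describes groups of 6-8 fathers. The threat-of-harm reason and the crisis referral apply to both arms. Moves and job loss, which Section 13 foresees, are likelier sources of missing outcomes. Fathers removed for distress may also decline the assessment, so the fix may recover only some of them.

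Most of this stands, and it keeps the point minor. It does not remove the ambiguity: two coordinators could act differently in good faith.

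A reader might infer three stronger claims, none of which the documents support:

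- **That Section 14 contradicts Section 12, or that follow-up definitely ends.** The text is ambiguous, not contradictory, and the consent pages, which were not available, may say more.
- **That the son's assessment also stops.** Sons are separate participants who attend no sessions, and no text ends a son's assessment because his father was removed.
- **That the bias favours HoMBRES.** Removal and referral could push either way.

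**Conclusion.** The point holds as a minor one. On its natural reading, Section 14 lets a removal tied to the sessions end collection of the only follow-up outcome, and that does not fit analysis by initial assignment.

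Under the stated assumptions, a few removals are negligible: 5.0-5.7% for 1 v 0 up to 4 v 2. A lopsided 8 v 0 gives 6.4-17.7%, somewhat less with baseline adjustment if baseline explains part of the gap. It would be tempting to say that the problem begins at 10% of one arm, but that is not a general threshold. It rests on an assumed unadjusted gap of about 1 SD. At 0.5 SD, passing 10% type I error takes 15 v 0 (19% of the arm); at 1.5 SD it takes 6 v 0. The documents support no particular removal rate, gap or direction. Clustering, ignored here, would raise the SE and reduce the relative bias.

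**What to change.** In Section 14, define stopping sessions and withdrawing from data collection as separate events. State that after the PI stops a father's sessions, the planned 6-month assessment is still sought, by phone if needed, unless he declines further data collection. Leave the PI's existing criteria and authority to stop participation as they are. Report PI removals and voluntary withdrawals separately, by arm and reason.

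A sensitivity analysis is optional. If one is done, it should cover all missing 6-month outcomes, not only those of removed fathers, and vary the assumed values in both directions, since the direction of bias is unknown.

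The cost is one or two protocol sentences, a matching consent line and two rows in the participant-flow report. The 6-month contact is already planned, and Section 10 allows it by phone. The downside is a few possibly sensitive contacts, since Section 15 warns that some questions may cause distress; the father's right to decline limits this.

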As described in section 7, participants will be recruited through a variety of methods including word of mouth, flyers, radio add, community agency collaborators as well as active outreach in the different activities in the community.

25) Local Number of Subjects

Aim 1: Sixty-eight (N=68) participants will be sampled in the focus groups (n=48) and the interviews (N=20).

Aim 2: The total number of subjects in the intervention will be 320 (160 father/son dvads).

Aim 3: To be determined

26) Confidentiality

The issues surrounding confidentiality are of supreme importance and sensitivity because highly personal clinical information will be obtained from the fathers and adolescent sons in Aim 2. Adult participants will provide written consent attesting consent to their understanding that the information they provide will be held as personal and confidential to the extent permitted by law. Youth will provide written approval to the assent form that explains the limits of confidentiality. Consent and assent forms will clearly state the right to refuse participation at any time. Further, the refusal to participate will not influence any of the services the adolescent or his/her family may receive. In addition to the confidentiality assurances, the participants in the study are protected by a Certificate of Confidentiality under section 301(d) of the Public Health Service Act (42 U.S.C. 241(d), authority delegated to the National Institutes of Health (NIH).

Regarding data and other records confidentiality, researchers will follow the UM established set of procedures designed to ensure the protection of confidentiality. All project staff will be specifically trained on issues of confidentiality. Due to the use of the web-based REDCap system we anticipate that there will not be any hard copies of data and all the documents pertinent to the study such as consent forms and contact information will be stored in a locked cabinet at the FIU Center for Research on US Latino HIV/AIDS and Drug Abuse (CRUSADA) offices overseen by CLaRO PI, [name] and protocol lead, [name]. Passwords are used to restrict entry into the REDCap database. There will be very few documents with identifying information (consent forms) and all documents with identifying information will be stored at the in locked file cabinets within a locked office in the PI office and the project director's office. It should be noted that in our years of clinical research (over 14 years), not a single incident of violation of confidentiality has occurred.

The technology system that will be used in the study will collect usage data that will be securely housed on the project servers. Data will be collected without requiring that the participant actively send them. Data collected in real-time do not contain names or identifying information, only case numbers. In addition, the system will require a

Page 19 of 23 Revised: March 23, 2020

IRB Study Number: Version HoMBRES de Famlia (HoMBRES) #1

password to see messages sent to the participant. Physical access to servers at the Data Center are controlled by security systems, intruder alarms, and monitored by the Department of Security video surveillance/recording systems. At FIU, the Data Center provides appropriate environmental control via HVAC systems, uninterruptible Power Supply and emergency generators to maintain power without interruption, The Data Center also provides secure backup for all data systems.

The study will be monitored by the CLaRO Study Monitoring Unit which is based at the UM School of Nursing and Health Studies. The Study Monitoring Unit will (1) verify compliance with regulatory requirements, (2) ensure that the Project Leads and staff (including those at community agencies) are fully informed of regulatory requirements and properly trained to perform the duties assigned, and (3) monitor procedures to prevent errors and minimize protocol deviations that can negatively affect quality of the data collected and compromise human subjects' protection. The project will have a quality assurance (QA) review: prior to initiation, upon conducting baseline procedures with the first wave of study participants; and bi-annually for interim reviews.

27) Provisions to Protect the Privacy Interests of Subjects

As explained previously, interviews will be done in a private setting chosen by the participant. Data will be entered to RedCap in a password protected IPad. Data will be only available to researchers approved by the IRB and to the study monitoring unit. Participants will be reminded of their ability to stop the interview or refuse to answer questions that make them uncomfortable. During the recruitment and consent/assent process, and prior to any data collection, participants will be assured that their information is confidential, and will only be accessed by study staff members. As described above, participants will sign a statement attesting to their understanding that their information will be kept private and confidential to the extent permitted by law. Participants know that they will be assigned unique case numbers (and that their names will not be used) to protect their identity. For telephone data collection, participant will be asked to choose a quiet and private area where he can answer questions while keeping confidentiality. Whenever, possible and as per participant preference, he will be interviewed via videoconference to increase the rapport and ensure privacy.

28) Compensation for Research-Related Injury N/A

29) Economic Burden to Subjects

Aim 1: Participants may incur costs associated with transportation to and from intervention sessions. However, most participants will live within walking distance to the program location. Participants will be compensated to offset their expenses. Aim 2: We do not anticipate that the participants will endure any financial cost as the recruitment, consenting, and intervention will be provided using digital venues and participants will be able to complete the study from their homes. To further prevent participants' financial burden, we will suggest free telephone applications such as WhatsApp. When the CDC recommends that social distancing is no longer necessary, consenting and interviewing may be done face to face as per participant request. Additionally, when social distancing restrictions are no longer active, UBER services would be available for participants who report transportation difficulties to get to interviews.

Page 20 of 23 Revised: March 23, 2020

IRB Study Number: Version HoMBRES de Famlia (HoMBRES) #1

FIU entered into an agreement with Uber Health to help with transporting research participants from their homes or work or preferred location to the research sites and return. According to Uber Health, they take healthcare patient and confidentiality seriously and already treat research participants in the same manner. To handle Protected Health Information (PHI) with appropriate care, they've built HIPAA compliance into Uber Health from the ground up. According to [name], CEO Clearwater Compliance, "In June 2017. we conducted a HIPAA Risk Analysis of the technical, physical, and administrative controls related to Uber Health's new dashboard and technology. Our team concluded that Uber Health has an unusually robust security environment involving numerous information security safeguards." Uber Health states that they have a HIPAA-trained Uber Health team dedicated to building technology for healthcare and that rider information is encrypted as a safeguard for handling PHI when ordering rides for participants. Uber signed a Business Associate Agreement (BAA) with FIU and under the BAA. Uber is committed to performing steps, which safeguard and protect PHI. When a driver receives an Uber Health trip request, it is indistinguishable from any other type of Uber request to protect patient privacy.

The internal infrastructure of the Uber's data storage:

"Uber Health applies an information security defense-in-depth strategy where layers of technical and administrative controls are deployed and then validated by user access and activity reviews, alerting, deployment of near-universal two-factor authentication, and use of encryption. Ongoing monitoring provides reasonable assurances that only authorized users have access to the Uber Health environment. Uber Health and Uber Technologies have implemented numerous information security safeguards that are considered industry best practices, including but not limited to: authentication, password management, expiring certificates, imaging, encryption, internal monitoring and reporting, role-based access and disaster recovery. Uber Health's ePHI is stored within a reputable, HIPAA-compliant thirdparty cloud environment to which physical access is highly restricted and monitored, and in transit ePHI in the Uber environment is subject to encryption and strict administrative and technical controls." In addition, Uber has controls in place to make sure only the necessary individuals within FIU can see participants' information. Administrators and billing contacts will only receive a sum total of the money spent on rides and a transaction list of each ride leading up to that amount. The coordinators within FIU who are arranging the rides would only be able to see the rides they order themselves and not of others.

30) Consent Process

Aim 1: All participants will provide their consent (or assent as applicable) prior to participating in the interviews and focus groups. Participants will be given a consent (or assent) form which will be read to them by a study team member in their preferred language (Spanish or English) as some of our participants have a very low literacy level. The consent process will either take place in a group or individual format. Participants will be encouraged to ask questions regarding any aspect of the study and the study personnel will answer these questions. Participants will keep a copy of the consent/ assent forms.

Aim 2. After potential participants are identified and screened, a meeting will be scheduled with the father-son dyads to complete informed consent/assent procedures and baseline assessments. Fathers and adolescents will be read the consent/assent forms for the reasons explained previously. Participants will be encouraged to ask questions regarding any aspect of the study and the study

Page 21 of 23 Revised: March 23, 2020

IRB Study Number: Version HoMBRES de Famlia (HoMBRES) #1

personnel will answer these questions. Once all questions are answered the participants will be asked to provide written approval to the consent/assent form. Once the minor turns 18 years old, a new consent form will be read and requested to provide written approval by such participant. In cases where the adult male (father) is not the legal guardian, written consent from the child's legal guardian will be required in addition to assent from the adolescent.

As result of the social distancing recommendations, eligible participants will be contacted via telephone, FaceTime apps, WhatsApp, telephone or video call to read the consent form. Consent will be read to eligible participants over the phone with two staff members present (one listening on the speakerphone who will sign as a witness to the consenting). The participant will also be given the option of having a witness on his side of the phone. If a potential participant agrees to participate in the study, he will provide verbal consent which will have the signature of the staff obtaining the consent and the witness. Then 2 copies of the consent with signatures will be emailed, texted or mailed as per participant choice of delivery. This will be sent with a stamped return envelope for the participant to sign and return to the research team. The same procedure will be used for the consenting of the legal representative and the assenting of the youth. Father-son dyads interviews (time and date) will be scheduled simultaneously, and they will be interviewed via phone separately in order to maintain confidentiality. A staff will conduct the interview with the father using any available venue for the participant (Phone or video conference). Since the adolescents are self-administering the questionnaire, they will receive a RedCap link to the questionnaire on their telephone, computer, tablet or IPad so they can respond to the measures. The adolescents will also be given the option of phone interview. A staff member will be available to guide the adolescent as well as answering any questions and ensuring completion. When CDC recommends that social distancing is no longer necessary, consenting will return to face-to-face process, however the interviewing may be done face to face or via phone as per participant's request. Participants already enrolled in the study prior to the social distancing requirement will be informed of changes to the protocol with a consent addendum which will be shared with them via telephone or web, depending on modality we are using with that participant.

Non-English-Speaking Subjects

For all aspects of this study, we will defer to language preference of the participants. The explanation of all aspects of the study (forms, procedures, measures and interventions) will all be available in either Spanish or English. Data analytic discussions and all reports will be in English. Back translations, whenever appropriate, will be conducted. Quantitative surveys will be conducted by the bilingual research team and staff in the preferred language of the participants (English or Spanish). We anticipate that survey protocols will be administered in Spanish for parents and English for the adolescents. Trained coders will transcribe interviews and focus groups in the language in which they were conducted. Data collected in Spanish will be coded using the codebook described below. We will construct the instrument in Spanish and will analyze the transcripts from each session in the original language to avoid second and third order level analysis. The HoMBRES de Familia Research Project will communicate with the male Latino farmworker population in a language that speaks to them—from a cultural and social perspective.

Waiver or Alteration of Consent Process (consent will not be obtained, required information will not be disclosed, or the research involves deception)

NA

Page 22 of 23 Revised: March 23, 2020

IRB Study Number: Version HoMBRES de Famlia (HoMBRES) #1

Cognitively Impaired Adults

NA

Adults Unable to Consent

NA NA

31) Process to Document Consent in Writing

We are requesting a waiver of signed consent/assent for Aim 1 as the procedures are of negligible risk and signing forms can be anxiety-producing in this population due to uncertain immigration legal status.

Written approval to the consent/assent will be collected for Aim 2, except for the modification described above for purpose of COVID-19 social distancing. After the study is explained and the participant verbally indicates that he understands, participants will provide written approval and date 2 copies of the consent or assent (youth) form. The research staff or interviewer will co- sign the forms. The participant will be given one copy of the signed consent form for his records, and the second copy will be stored in a locked cabinet at FIU offices.

32) Drugs or Devices

NA

Page 23 of 23 Revised: March 23, 2020
